8. DATA HANDLING

8.1 Data Protection and Storage Plan

The Data Operations Team and study staff within UHG R&D are responsible for adhering to the following Best Practices for Data Management:

Data Operations follows the standards of HITRUST for data management and data governance

1. Data always remains encrypted in transit and at rest.
2. Managed access with expiration dates.
3. Minimum use regarding dataset usage.

Access to protected data is limited to the Data Operations Team within UHG R&D

1. Data Operations does not participate in research efforts.
2. Data Operations uses identifiable data to match across all data sources and issue surrogate keys.
3. Data Operations de-identifies and lands the matched data in the Data Factory for use by the organization in research efforts.

Restricted research project data can be isolated from other data sources

1. Data Operations uses the Master Data Management (MDM) asset which contains logic to identify sources and matched people that have restrictions for use.
2. The MDM de-identified surrogate key crosswalks are maintained in separate restricted datasets using the restricted flag as referenced in #1 above.
3. Data operations user groups allow access to be limited to only those users with permission to work with restricted data. The restricted data is managed by the Data Operations to ensure isolation from other data sources.
4. Data for use in operations businesses is also isolated at the project level in the Person ID Management (PIM) asset. Only users with project level access may view the identifiable data associated with these restricted records.

8.2 Power Analysis

In this section, we detail the methodology and results for power analysis. To evaluate treatment effects based on the discrete clinical endpoint (hospitalization rate at Day 28 post infusion), we compared the proportion of events (i.e., prevalence rate or COVID hospitalization rate) between treatment and matched-control group which is our primary objective of interest. Specifically, we are interested in testing the efficacy (superiority) of treatment effects, which can be written formally in one- or two-sided hypotheses. Assume the null hypothesis is two-sided. We performed the power analyses based on a 5% level of significance (Type-I error) for a set of values of power (i.e., 0.75, 0.80, 0.85, 0.90, 0.95). We obtained the minimally required sample size for multiple scenarios - (a) hospitalization rate (0.20, 0.25, 0.30, 0.35) based on BCRT and CDSM data (b) different possible efficacy rates (reduction rates in hospitalization after using treatment). We used multiple methods - (i) a two-sample proportion test in detecting a difference between two binomial probabilities (Casagrande, 1978) (Fleiss, 1980) and (ii) McNemar's test (Agresti, 2003).

The former test statistic follows Gaussian distribution asymptotically exploiting large sample theory and the latter is designed to test categorical shift (or association) in responses (hospitalization rate in our example) between treatment and control group where the idea is to cast the data into a 2 x 2 contingency table. While both these methods provide competitive and

[figure not shown]
comparable results, reported below are the results based on the first method, a two-sample proportion test with continuity correction. The one-sided hypothesis requires a smaller sample size than that of a two-sided test.

Figure 2 illustrates the sample size required with a case and control ratio being 1:1 for different hypothetical scenarios. As expected, when the true prevalence rates between treatment and control groups are small, it requires a larger sample size to detect a statistically significant difference. As reported in the Lilly SARS-CoV-2 Neutralizing Antibody Program Update, the hospitalization rate for the treatment (i.e., LY-CoV555 Mono) group drops by 75% compared to that of the placebo group. Based on this relative change, we will need a total sample size less than 1,000; follow the power curves (i.e., corresponding to 0.10 Type-II error) in Figure 2 top-right panel with 75% (approximately) reduction rate. For example, using the COVID hospitalization rate of 25%, reported below in Table 2, are the minimum COVID diagnosed patients required to detect varying differences between the proportions at a 5% level of significance with 90% power of rejecting a two-sided null hypothesis.

Table 2: A case study for baseline hospitalization rate of 25%.

Absolute differences (assumed) between prevalence rates of treatment and control group (% reduction from baseline rate)	Total sample size (treatment and control as 1:1)
---	--

0.24 (95%)	97
0.21 (85%)	129
0.19 (75%)	175
0.16 (65%)	244
0.14 (55%)	355
0.11 (45%)	550
0.09 (35%)	940
0.06 (25%)	1,899
0.04 (15%)	5,416
0.01 (5%)	49,900

[figure not shown]

Figure 2: Power analyses at 5% level of significance for six scenarios with baseline COVID hospitalization rates of 15% (top-left), 20% (top-right), 25% (middle-left), 30% (middle-right), 35% (bottom-left), and 40% (bottom-right) based on CDSM and BCRT databases. Varying prevalence rates along with reduction (in parenthesis) in hospitalization from baseline (i.e., control group) for the treatment group are considered (X-axis) as 95% to 5%. Reference lines corresponding to 5,000 and 2,000 sample size are drawn for convenience of comparison.

8.3 Future Utilization

There are no samples being collected from the participants in this study and therefore, there will be no residual biospecimens. The data collected from this study, combined with appropriate health record and claims data, will be retained for additional analysis/utilization if determined appropriate (this will require a separate protocol submission or a modification to this existing study to outline the additional analysis occurring and the associated plan to retain confidentiality for the data being utilized).

8.4 Publication Plan

There is intention to publish the findings of the study in partnership with Eli Lilly and Company. Any data used for publication purposes will be presented in aggregate and will not identify individual participants.

1. QUALITY CONTROL, MONITORING AND REPORTING

9.1 Issues Management Plan

There are two potential sources of issues that may be experienced during participation in the study. We will limit monitoring and reporting to those participants who receive Bamlanivimab (LY3819253).

Participant Reported Issues:

Participants will track daily how they are feeling from Day 1 post-infusion (their baseline of how they are currently feeling) through Day 28 (end of active study). This tracking will be conducted via the ProtectWell application and will have two potential outcomes: 1) Participant indicates they are feeling the same or better (no further follow-up needed) or 2) Participant marks they are feeling worse and there will be a reminder notification via ProtectWell if they are experiencing severe/life-threatening symptoms to seek help and it will trigger a clinical follow-up with that participant (clinical follow-up will occur via phone outreach to result in a discussion with the participant). Based on the discussion, one of the following may occur: 1) participant is OK to remain at-home and on study or 2) participant should seek medical care and are marked as meeting an end point (and we will track outcome of what they needed and if they required hospitalization).

In addition, when speaking to the participant, the clinical team will attempt to ascertain if the issue is: 1) related to worsening COVID-19 symptoms, 2) a potential side effect of Bamlanivimab (LY3819253) or 3) any other unanticipated event that might occur during active study participation. If the issue is potentially related to a side effect of Bamlanivimab (LY3819253), the clinical team will engage the UHG R&D clinical support team (internal R&D team with nurse management oversight for connection for clinical consult when needed) and that project support team will report the issue to Eli Lilly and Company if determined by the PI or delegate to be an unexpected and likely related to the study event (related to receiving Bamlanivimab (LY3819253) – not related to COVID-19 infection which is not due to participating in the study).

Optum Infusion Reported Issues:

Optum Infusion has three potential touch points with the participants in the study:

Pre-Infusion:

- Any issues that arise during the contact call to set up shipping the drug and scheduling the at-home infusion visit
- Any issues that arise during the period from scheduling the at-home visit through to infusion visit

Infusion Visit:

- Collection of pre, during and post-infusion information and any adverse reactions or other reported symptoms (this is formally documented on the case report form (CRF) and is compiled and reported to the UHG R&D project support team (and the project report team may determine that Eli Lilly and Company needs to be informed of information on the CRF and will follow-up on that accordingly – events that are likely to be related and/or unexpected in severity/frequency will be reported to Lilly).

Post-Infusion:

Optum Infusion will provide contact information for the participants at the infusion visit and the participant may opt to use this for outreach (they will also have ProtectWell and the outreach number provided on the consent document) and the Optum Infusion representative will discuss the issue with the participant and make a determination if they can give descriptive advice or if they need to loop in the UHG R&D project support team to engage either the UHG clinical team (if deemed appropriate) or to inform Eli Lilly and Company of the issue and expected plan of action to address the issue.

- Any issues reported via either mechanism will be documented, assessed whether the event was related to study drug.
- For Serious Adverse Events (SAEs) – events resulting in hospitalization, substantial action being required (without hospitalization) or death – events must be reported/assessed and submitted to the IRB for consideration within 72 hours
 - For any serious adverse events that meet the following criteria and result in any of the outcomes listed – these will be reported to Lilly upon discovery within 24 hours:
 - Suspected adverse reaction
 - Serious
 - Unexpected
 - And result in the following outcomes (i.e. serious adverse events):
 - Death
 - Life-threatening adverse drug experience (meaning determined related to bamlanivimab)
 - Inpatient hospitalization or prolongation of existing hospitalization (for > 24 hours)
 - Persistent or significant incapacity or substantial disruption of the ability to conduct normal life functions
 - Congenital anomaly/birth defect (not likely to apply to this protocol)
 - Important Medical Event (IME) that may not result in death, be life threatening, or require hospitalization may be considered a serious adverse drug experience when, based upon medical judgment, it may jeopardize the patient or subject and may require medical or surgical intervention to prevent one of the outcomes listed in this definition
 - For Adverse Events (AEs) – events must be reported/assessed and submitted to the IRB for consideration within 10 business days
 - For any events – if event is likely related to Bamlanivimab – event will be assessed by the PI and medical review team and findings will be reported to Lilly in alignment with the FDA EUA requirements

Interim Safety Analysis and FDA Reporting:

During the period of active at-home infusions (including post-infusion observation period), data will be compiled and assessed real time for any unanticipated problems or other serious adverse events that may require reporting to either Lilly and/or the FDA. In addition, after infusion of approximately 50 to 100 participants (up to 100 participants), an interim safety report will be compiled for Lilly and the FDA, per the FDA's request in the IND correspondence letter received on December 23, 2020. Given the design of the study and the fact that there is a 10-day from symptom onset window to infuse participants after confirmed COVID-19 diagnosis with a constant rolling list of eligible participants to have an at-home infusion of Bamlanivimab scheduled – the number of participants infused will be at least 50 and no more than 100 when this interim report is filed with Lilly and the FDA. Enrollment of new participants to enter the first stage of the trial (symptom screening) will pause while FDA review of the interim safety data occurs and enrollment will not recommence until FDA concurrence of enrollment expansion is received.

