4.4 Metrics and Variables

The primary outcome of interest is COVID-related hospitalization rate in study participants and matched controls. We list all potential covariates in two phases. Phase I covers historical data and Phase II includes post COVID-19 diagnosis information. Phase I historical data will be collected for both study participants and matched controls. Phase II post-COVID 19 diagnosis data has two parts: data elements to be collected for both study participants and matched controls (Phase II.A), and data elements to be collected for only study participants (Phase II.B).

Phase I - Historical data: Study participants and matched controls:

1. COVID-19-related information:

- Symptomatic or asymptomatic during COVID-19 test
- Number of COVID-19 cases per 10,000 people in the county of residence during COVID-19 test (if available)
- Number of COVID-19 deaths per 10,000 people in the county of residence during COVID-19 test (if available)

2. Demographic:

- Age as of 2020
- ZIP code of residence (may or may not be used for identifying matched controls)
- Urbanization of residence in a zip code level (urban, suburban, rural)
- Region/State of residence
- Race
- Gender
- Flag determining whether a patient resides in a nursing facility (or has been staying in a nursing facility currently) – determining patient does not live at home

3. Insurance:

- Line of business (should be mostly Medicare)
- Dual-eligibility status
- Continuous member enrollment in 2019
- Continuous member enrollment in 2020

3. Comorbidities in 2019:

- History of chronic kidney disease
- History of diabetes
- History of immunosuppressive disease
- History of cardiovascular disease
- History of hypertension
- History of chronic obstructive pulmonary disease/other chronic respiratory disease

- Elixhauser score for readmission
- Historical flag for all other associated comorbidities used in computing Elixhauser score (i.e., 29 categories like kidney disease, cancer etc.)

4. Immunosuppressive treatment

- History of receiving immunosuppressive treatment (6 months prior to date of COVID diagnosis)

Phase II.A: Post COVID-19 diagnosis data: Study participants and Matched controls

- Date of COVID-19 diagnosis test
- Type of COVID-19 diagnosis test (e.g., PCR, Antigen)
- Hospital admission date (if patient is hospitalized)
- Type of hospital admission (measuring level of trauma) (if available)
 - Through ER (if any)
 - With ICU transfer (if any)
 - With ventilation (if any)

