4.5 Endpoints

The following definitions of endpoints hold for all analyses described in this statistical analysis plan. For study participants, we define the study endpoint as 28 days after date of the Bamlanivimab infusion. This holds for both outcomes of COVID-related hospitalization with or without time consideration (i.e., no censoring vs censoring at Day 28). For example, if a study participant hasn't been hospitalized due to COVID-19 within 28 days after COVID-19 diagnosis, we'll treat the binary response of COVID-19 hospitalization as 0 without time consideration. However, with time consideration, it becomes right-censored since this participant may be hospitalized 29 or more days after COVID-19 diagnosis and our observation period is 28 days after COVID-19 diagnosis. More details are described in Section 5.8.1.3. For the pool of potential controls, we define the study endpoint as 28 days after a synthetic date of treatment. We will randomly select a number from the distribution of number of days after date of symptoms onset in study participants to identify an index date with which to define 28 days post infusion where we will monitor claims and EMR data for hospitalizations and mortality.

Commented [WWY14]: Should be the pool of controls which was before PS matching.

Figure 3 illustrates the timeline for study participants and controls to ensure alignment on an index date for symptoms onset and the follow-up period. Since the control group will not have an infusion date associated with them, we will randomly select a number from the distribution of number of days after date of symptoms onset in study participants to identify an index date with which to define 28 days post infusion where we will monitor claims and EMR data for hospitalizations and mortality.

[figure not shown]

Figure 3. Illustration of the timeline for study participants and controls.

For patients who do not experience a COVID-19 related hospitalization by Day 28 following the date of infusion or synthetic treatment, a censoring date is defined as the earliest of 28 days following the date of treatment, or for study participants, the early discontinuation date due to lost to follow-up.

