5.8.1 Main analytical approach

5.8.1.1 Pre-matching identification of risk factors as matching covariates

Before matching, we will select covariates to be included in the propensity score estimation model. Covariates that are predictive of both treatment status and the outcomes and covariates that are associated with the outcomes will be selected to estimate propensity score. To do so, we will first conduct a literature review to identify the risk factors that are associated with COVID-19 hospitalization. The findings from the literature review will help create a list of variables on which treatment and control groups will be matched.

Consider a binary response taking a value of 1 if a patient is hospitalized due to COVID-19, and 0 if a patient is tested positive for SARS-CoV2 but does not have a record of subsequent COVID-related hospitalization (hospitalization within 38 days of a positive test). We include risk factors such as demographic (e.g., gender, age, race, geographical area such as state or county), comorbidities (Elixhauser scores related comorbidities such as diabetes, metastatic cancer, heart diseases, obesity, coagulopathy, and so on), and other potential clinical attributes as available in

the identification of the appropriate matched cohort. These risk factors will also include all clinically identified variables by Eli Lilly to define moderate and high-risk groups. We will run this step three times with three datasets; specifically, we consider:

- a. Iteration 1: This is based on retrospective data available in-house consisting of Medicare Advantage (MA) members, aged greater than or equal to 65, and COVID diagnosed. We will exploit BCRT, CDSM, and UHC Claims data sources. The study cohort here is a broader population than the study participants.
- b. Iteration 2: This is solely based on data associated with study participants. We will exploit risk factors from UHC Claims and study enrollment information from Optum infusion pharmacy data.
- c. Iteration 3: This is based on information of both the general MA population and study participants –retrospective and prospective data in Iteration 1 and Iteration 2, respectively. We will exploit COVID labs and hospitalizations from BCRT and CDSM, risk factors from UHC Claims data, and study enrollment information from Optum infusion pharmacy data.

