Understanding the COVID-related hospitalization rate at Day 28 (binary endpoint) between study participants and matched controls is the key primary objective. We consider the analysis in combinations of with/without time-related outcome and with/without covariate adjustment. A single model will be selected and documented prior to accessing outcome data with the focus of including covariates expected to be strongly related to outcome based on other studies.

First, consider the simplest scenario without covariates adjustment and time-related outcome; we will use nonparametric McNemar's test to compare the hospitalization rate at Day 28 between the treatment and control groups at the level 0.05. Separately, for those who are not admitted due to COVID at Day 28, we will treat their non-hospitalization as a censored response after Day 28, instead of assuming no COVID hospitalizations after Day 28. Without covariates adjustment, we will draw Kaplan-Meier curves and perform log-rank test to compare the equality of curves implying similar cumulative incidence of hospitalization between the treatment and control groups over 28-day period.

Next, consider covariates adjustment, this will allow us to compare hospitalization rate between treatment and control groups given a subset of matching covariates or covariates not included in matching. Without any covariate adjustments, treatment effect might be subject to potential confounding variables. We will construct a multiple generalized linear model with fixed or

Commented [XM40]: Please specify the link, dist

mixed effects and a logit link to examine if the hospitalization rate differs between study participants and matched controls after adjusting demographics (e.g., age, gender, etc.) and comorbidities (e.g., Elixhauser conditions). The appropriateness of using mixed model will be determined by information criteria (AIC or Bayesian information criteria (BIC)) values.

Considering the time component in the response, we will use Cox proportional hazard model, accelerated failure time model and other survival models. Proportionality assumption of the Cox model will be checked by Schoenfeld residuals. Method selection will depend on if model assumptions hold in our data.

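### Protocol 9.1 labels a referral to care as an end point, and no common rule defines COVID-related hospitalization in the two arms

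*Protocol*

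**What the plan says.** **The endpoint.** Protocol 4.4 states: "The primary outcome of interest is COVID-related hospitalization rate in study participants and matched controls". SAP 5.8.1.3 makes it binary: "Understanding the COVID-related hospitalization rate at Day 28 (binary endpoint) between study participants and matched controls is the key primary objective". SAP 4.5 sets the censoring rule "For patients who do not experience a COVID-19 related hospitalization by Day 28 following the date of infusion or synthetic treatment": the earlier of 28 days after treatment or, for study participants, loss to follow-up.

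**The call.** Protocol 9.1 limits monitoring to people who received the drug. A participant who reports feeling worse is phoned. The call ends either with the participant staying at home and on study, or with "participant should seek medical care and are marked as meeting an end point". The text continues in parentheses: "and we will track outcome of what they needed and if they required hospitalization". During the conversation "the clinical team will attempt to ascertain if the issue is: 1) related to worsening COVID-19 symptoms, 2) a potential side effect of Bamlanivimab", or some other unanticipated event.

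**Where events come from.**
- Treated arm: self-report in the short term and records or claims in the long term (Protocol 2); patient report plus BCRT, with claims later as a consistency check (Protocol 6.5.2); infusion pharmacy data plus BCRT (SAP 5.8.1.3), with BCRT described as complementary (SAP Table 1).
- Controls: UHC claims and Optum EMR inpatient records (SAP 5.8.1.3).

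**The definition.** SAP Appendix 1 holds the definitions and codes. It covers COVID-19 tests, Elixhauser conditions and immunosuppressive prescriptions, and has no rule or code list for a COVID-related hospitalization.

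**The concern.** Two points need to be separated.

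First, the protocol uses the term end point for advice to seek care, while every efficacy section uses it for hospitalization. A data manager who builds the hospitalization flag from the study file would find participants marked as having met an end point without having been admitted.

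Second, whether an admission is COVID-related is a judgement about cause, and no rule governs it. In the treated arm part of the information reaches the study through contacts with people who know the drug was given. Controls have no such contact and are classified from records alone. If the same admission could count in one arm and not in the other, part of the treated-control difference would reflect classification rather than the drug. Matching on baseline covariates does not remove that.

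**Working it through.** **1. Is the 9.1 mark the endpoint?** Set side by side, the passages say it is not. The sentence that creates the mark tracks hospitalization separately. The data-collection lists (Protocol 6.4 and SAP 4.2, item 7) name a recommendation to seek care and a need for hospitalization as different actions. The analysis variable in SAP 5.8.1.3 is a flag for COVID-19 related hospitalization over Days 1 to 28. So the wording conflicts, but no analysis takes the mark as input.

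**2. Does the cause noted on the call decide the endpoint?** No document says so. The use stated for it in 9.1 is reporting of possible drug-related events. But no document says what decides it instead.

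**3. Could one rule serve both arms?** SAP 4.7, Phase II.A, lists admission date and primary, secondary and tertiary diagnosis codes for both groups, from BCRT for participants and from Optum EMR or BCRT for controls. The fields exist. What is missing is the rule, and a statement that it overrides contact-based information.

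**4. Illustration of sensitivity.** The documents give no misclassification rate, so every share below is an assumption. The base is the SAP 4.4.2 scenario: 1,000 per group, 15% against 10%, two-sided 0.05. The approximation ignores pairing and has no continuity correction:

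power = Φ{[|p1 − p2| − 1.96·√(2m(1 − m)/n)] / √([p1(1 − p1) + p2(1 − p2)]/n)}, with m = (p1 + p2)/2.

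*The plan's own figures.* For 15% against 10%, m = 0.125 and power = Φ[(0.05 − 1.96 × 0.01479)/0.01475] = 0.92. A power of 0.80 needs 686 per group (726 with continuity correction), so the SAP's statement that 1,000 suffices for 0.8 holds. Table 2 also reproduces to rounding; for example 176 against the stated 175 for a 75% reduction from 25%. The sample-size figures are not in dispute.

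*(a) Treated admissions attributed to another cause.* No true effect, 15% in both arms; observed treated rate = 15% × (1 − g).

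| g | Treated rate | Chance of a false significant benefit |
|---|---|---|
| 10% | 13.5% | 0.16 |
| 20% | 12.0% | 0.50 |
| 30% | 10.5% | 0.86 |

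*(b) Control admissions not recognised as COVID-related.* True rates 15% and 10%; observed control rate = 15% × (1 − h).

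| h | Control rate | Apparent reduction | Power |
|---|---|---|---|
| 0 | 15.0% | 33% | 0.92 |
| 10% | 13.5% | 26% | 0.68 |
| 20% | 12.0% | 17% | 0.30 |
| 30% | 10.5% | 5% | 0.06 |

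*(c) The 9.1 mark counted in error.* True rates 15% and 10%; observed treated rate = 10% + 90% × f, where f is the share of non-hospitalized treated participants who are marked.

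| f | Treated rate | Apparent reduction | Power |
|---|---|---|---|
| 1% | 10.9% | 27% | 0.78 |
| 2% | 11.8% | 21% | 0.56 |
| 3% | 12.7% | 15% | 0.32 |
| 5% | 14.5% | 3% | 0.05 |

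Case (a) favours the drug; (b) and (c) work against it. Nothing in the documents says which applies, or whether any does.

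**The case against.** The best defence is that 9.1 is a safety-management section with loose wording, and that efficacy is defined elsewhere and consistently as hospitalization. That stands. It rules out several stronger readings.

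- *The call sets the treated-arm endpoint.* A reader might infer this from the mark and from "the clinical team will attempt to ascertain if the issue is: 1) related to worsening COVID-19 symptoms". The efficacy analysis uses a hospitalization flag, and the cause question is put about an issue raised by phone, not about an admission. The protocol's symptom form also says that inpatient hospitalization is already being checked for the primary efficacy endpoint, which ties that endpoint to admission rather than referral.
- *Referred participants leave follow-up.* A reader might infer this from the contrast with staying on study. The same sentence promises outcome tracking, and SAP 4.5 does not censor at referral.
- *A competing 38-day endpoint rule exists.* SAP 5.8.1.1 has the wording "does not have a record of subsequent COVID-related hospitalization (hospitalization within 38 days of a positive test". It belongs to the response variable of the pre-matching risk-factor model, and 38 days equals the 10-day infusion window plus 28 days. It does not define the primary endpoint.

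The defence can add that the treated arm also has records: BCRT, and under Protocol 6.5.2 claims as a later check. That narrows the asymmetry but does not close it. BCRT is ranked as complementary in SAP Table 1, the later claims are only a consistency check, and no text says which source prevails or how cause is decided. The missing definition does not arise from 9.1, but it remains.

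**Conclusion.** The point holds in limited form. The term end point in 9.1 conflicts with the primary endpoint and must be reconciled with it. COVID-related hospitalization has no definition in either document, and its ascertainment rests partly on unblinded study contacts in one arm and on records in the other. Differential attribution is therefore possible. It is not demonstrated, and its direction and size cannot be determined from the documents.

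The tables show only that modest differences in classification would matter at 1,000 per group. They rest on assumed shares and on the SAP's 15% and 10% rates. A reader might take them as a forecast of a false benefit or of a masked one; the documents support neither. No view is taken here on when a participant should be advised to seek care.

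**What to change.** 1. **Protocol 9.1 and SAP 4.5.** Reconcile the two. Record the 9.1 mark as a medical-care referral that is not the primary endpoint, and state that outcome tracking continues to Day 28.
2. **SAP 4.5.** Define COVID-related status by one pre-specified diagnosis-code rule, applied identically to inpatient records in both arms with the code fields in SAP 4.7, and independent of any cause noted under 9.1. Add the code list to Appendix 1.
3. **SAP 5.8.2 and Table A10.** Add all-cause inpatient admission through Day 28 as a pre-specified sensitivity analysis. It needs no attribution of cause, and the listed sensitivity analyses do not include it.

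**Cost.** Wording changes, a short code list and one more analysis on fields already listed. All-cause admission dilutes a true effect with unrelated admissions. Counting a COVID code in any of the three positions will include some incidental COVID-positive admissions, so results with the code in the primary position only should be shown alongside. SAP Table 1 lists claims and BCRT for UHC members only. SAP 5.1.1 restricts the analysis populations to UHC members, but SAP 5.8.1.2 also plans to match non-UHC participants; if they are analysed, the SAP must say which inpatient record the rule is applied to.
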